#### 8.1.1 Step by Step Instructions

1. The eBx patients will be determined first. They are called consecutively based on the length of follow-up required by this protocol.

2. As patients are called back for consenting and follow-up visits begin, the patients treated with Mohs are called consecutively and asked to come back who match those treated with eBx.

#### 8.2 Long-term Follow-up Visits

Each patient agreeable to participating in this study will be asked to return for an office visit for prospective data collection. There may be up to two (2) visits over the next years.

Since the subjects have already received treatment, the study cannot include a randomization design. Each lesion from the eBx treatment group will be matched to a lesion treated with Mohs surgery. The variables used for matching will be:

- Calendar year of treatment for equivalent follow-up
- Patient age bracket [Attempt to ensure 15-year brackets or less]
- Lesion diagnosis (BCC or SCC)
- Lesion size range (< 1 cm,  $\geq$ 1 and <2 cm,  $\geq$ 2 cm and <3 cm,  $\geq$ 3 and  $\leq$ 4 cm)
- Lesion Location

It is not expected that there will be an equal number of patients treated with eBx and Mohs at each site, as some practices may not use both types of treatment modalities. To ensure that a minimum of 293 lesions are matched, the participating sites will be asked for a list of all patients treated approximately 2 to 4 years prior to study onset including the variables being used for matching. The study sponsor will then compare all the available data from the participating sites and notify each site which patient and lesion data will be included in the study.

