SECONDARY ENDPOINTS	
 
Comparison of long-term toxicities related to eBx vs. Mohs treatment;
 
Comparison of long-term cosmetic outcomes for lesions treated for NMSC with eBx vs. Mohs;
 
Comparison of Chronic toxicities;
 
Comparison of Patient Reported Outcomes (PRO) using a patient survey.
 
	
ESTIMATED STUDY PERIODFollow-up Visits #1: August 29, 2016 – August 31, 2017 Data Collection & Data Entry: August 29, 2016 – September 31, 20		
	Prospective Follow-up Visit #2: August 31, 2017- January 31, 2018 Data Entry: August 1, 2017 – February 28, 2018	
SPONSOR & FUNDING PARTY	Xoft – a subsidiary of iCAD, Inc. San Jose, CA	
STATISTICAL ANALYSESXoft – a subsidiary of iCAD, Inc. San Jose, CA		
STUDY MANAGEMENT	Eminence Clinical Research, Inc. Colorado Springs, CO	
ELECTRONIC DATA CAPTURE	Eminence Clinical Research, Inc. Colorado Springs, CO	
MEDICAL WRITING ASSISTANCE	Eminence Clinical Research, Inc. Colorado Springs, CO	

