#### 8 METHODOLOGY

#### 8.1 Identifying the Population

The first phase of this study will be to identify patients who completed treatment with eBx or Mohs treatment approximately 3 years ago or more prior to study onset and collect history and demographic data, and eligibility and treatment planning and treatment data retrospectively from the patient records and on source worksheets to complete a matched pair cohort study comparison.

This phase will include a review of the site's patient medical records to determine if the source documentation contains the variables that are needed to determine eligibility and which will be used in the endpoint analyses. These variables include:

- Patient Age (within  $\leq 15$  year brackets)
- Pathology report for evidence of:
  - Lesion size (cm)
  - Lesion diagnosis (BCC, SCC)
- Last treatment date for each location
- Lesion location (e.g. face, extremities, neck, nose, scalp, torso)
- Toxicities at time of prospective follow-up visit

Matching will be performed according to:

- Calendar year of treatment for equivalent follow-up
- Patient age bracket [15-year brackets or less]
- Lesion diagnosis (BCC, SCC)
- Lesion size range (< 1 cm,  $\geq$ 1 and <2 cm,  $\geq$ 2 and <3 cm,  $\geq$ 3 and  $\leq$ 4 cm)
- Location according to the methodology below:
  - o Scalp
  - Face (includes neck)
  - o Nose
  - o Ear
  - o Torso
  - Upper extremities (Arms, hands, fingers)
  - Legs (Thighs, lower leg, feet, toes)

Data Collected Prospectively:

- Cosmesis rating by physician
- Cosmesis rating by the patient
- Recurrence of cancer
- Chronic toxicities
- Patient reported outcomes (PRO) survey

Patients who return for long-term follow-up will be required to provide informed consent for both the retrospective data and the prospective data that are collected at the time of the visit.

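### Sections 8.1.1 and 8.2 do not agree on how Mohs controls are chosen, and neither fixes an order, a lock date or blinding, so outcome-aware selection is not excluded

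*Combined protocol and SAP*

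**What the plan says.** Two passages of the protocol describe how lesions enter the comparison.

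- **Section 8.1.1** takes the eBx group first: "The eBx patients will be determined first. They are called consecutively based on the length of follow-up required by this protocol". For the comparator, at the time when call-backs and visits are starting, "the patients treated with Mohs are called consecutively and asked to come back who match those treated with eBx".
- **Section 8.2** has each site supply a "list of all patients treated approximately 2 to 4 years prior to study onset including the variables being used for matching". The sponsor's task is next to "compare all the available data from the participating sites and notify each site which patient and lesion data will be included in the study". This covers both groups. The stated reason for central matching is that some practices may not use both treatments.

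Four other places bear on who chooses and what that party could see.

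- The Synopsis (Section 2) gives "Xoft – a subsidiary of iCAD, Inc. San Jose, CA" both as sponsor and for the statistical analyses. Section 5 identifies eBx as that company's system.
- Section 7.1 provides for collecting whatever data already exist in the patient's record.
- Section 8.1 has the first-phase record review look for "variables that are needed to determine eligibility and which will be used in the endpoint analyses", and its list includes "Toxicities at time of prospective follow-up visit".
- Table 1 (Section 12.1) puts recurrence on the prospective follow-up form only.

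**The concern.** The study is not randomised, so matching is its main protection at the design stage. Matching protects the comparison only if controls are chosen without sight of their outcomes. Here the party that decides on inclusion has an interest in one of the two treatments, and the plan leaves it discretion wherever more than one Mohs lesion fits. The patients were treated years earlier, so a chart may already record a recurrence. If knowledge of that kind influenced the choice, the recurrence difference would shift, and no later analysis of the selected lesions could recover the unselected comparison.

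**Working it through.** **1. The passages side by side**

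| Question | Section 8.1.1 | Section 8.2 |
|---|---|---|
| Who acts | Caller not named | Sponsor decides and notifies sites |
| Order among eligible Mohs lesions | Consecutive, with no order defined across sites | None stated |
| Timing | As visits begin | None stated |
| Date the list is closed | None stated | None stated |
| Selector kept from outcomes | Not stated | Not stated |

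Several eligible lesions per eBx lesion are plausible because the matching cells in Section 8.1 are broad: calendar year, age brackets of up to 15 years, BCC or SCC, four size bands and seven locations. Section 8.2 makes the age bracket an aim only. Matching can run across sites, so a consecutive order within one site does not settle which site's lesion is used.

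**2. The plan's sample size**

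Inputs (Section 12.2): recurrence 1.5%, margin 2.5 percentage points, power 80%, alpha 0.05. Equal true rates and independent groups are assumed.

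n = (z_alpha + z_power)² × 2p(1 − p) / margin²

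- One-sided 0.05: (1.645 + 0.842)² × 2 × 0.015 × 0.985 / 0.025² = 292.3, so 293. This reproduces the plan.
- One-sided 0.025: (1.960 + 0.842)² × 2 × 0.015 × 0.985 / 0.025² = 371.1, so 372. This does not.

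One-sided 0.05 is therefore the main case below. One-sided 0.025 is shown too, because Section 12.2 says all tests are two-sided at 0.05.

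**3. How few events decide the result**

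Expected recurrences per group: 293 × 0.015 = 4.4. Margin in lesions: 293 × 0.025 = 7.3.

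Take 4 Mohs recurrences. The Wald upper bound is d + z × SE, with d = (eBx − Mohs)/293 and SE² = p₁(1 − p₁)/293 + p₀(1 − p₀)/293. Non-inferiority passes if the bound is below 0.025.

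- One-sided 0.05, eBx 6: 0.00683 + 1.645 × 0.01070 = 0.0244, pass.
- One-sided 0.05, eBx 7: 0.01024 + 1.645 × 0.01120 = 0.0287, fail.
- One-sided 0.025, eBx 5: 0.00341 + 1.960 × 0.01016 = 0.0233, pass.
- One-sided 0.025, eBx 6: 0.00683 + 1.960 × 0.01070 = 0.0278, fail.

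The Farrington-Manning score statistic is (d − 0.025)/SE, with SE taken at the estimates constrained to a difference of 0.025:

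- eBx 4: (0 − 0.025)/0.01180 = −2.12, passes at both levels.
- eBx 5: (0.00341 − 0.025)/0.01195 = −1.81, passes at one-sided 0.05 only.
- eBx 6: (0.00683 − 0.025)/0.01211 = −1.50, fails at both.

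So the limit with 4 Mohs recurrences is 6 (Wald) or 5 (score) at one-sided 0.05, and 5 or 4 at one-sided 0.025. By Wald at one-sided 0.05, going from 4 to 5 Mohs recurrences leaves the limit at 6; going to 6 moves it to 7.

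**4. Illustration of what selection could do**

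Set the true rates at the margin (eBx 4.0%, Mohs 1.5%), sum the two binomial distributions with 293 lesions each, add k recurrences to the Mohs count, and apply the Wald rule. The values of k are assumptions; the plan gives nothing from which to estimate them.

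| Mohs recurrences added by selection | False non-inferiority, one-sided 0.05 | One-sided 0.025 |
|---|---|---|
| 0 | 6.9% | 3.5% |
| 2 | 13.6% | 7.7% |
| 3 | 18.4% | 10.7% |

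**The case against.** The strongest case is that the plan describes a workable sequence: sites send lists, the sponsor cross-matches them, and sites call the matches consecutively. Section 8.2 gives a practical reason for central matching, and Figure 1, which is not shown in the text available, may set out the order. This reading is reasonable, so the two passages are an unreconciled ambiguity and not a proven contradiction. Even in sequence, though, they supply no rule among several eligible lesions across sites.

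A reader might infer that Section 8.2 lets the manufacturer pick controls after eBx outcomes are known. The documents do not support that:

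- Section 8.2 sets no timing. The overlap with visits comes from Section 8.1.1, which implies at most that some eBx results may exist when Mohs patients are called.
- Early eBx results do not reveal which Mohs lesion has recurred. Choosing Mohs lesions by outcome would need Mohs outcomes.
- The data compared under Section 8.2 are most naturally the site lists, which are described by matching variables. The wording says what the lists include without limiting them to it.
- Follow-up toxicities cannot exist before the follow-up visit, so their place in the first-phase list looks like a drafting slip. They are also not the primary endpoint.
- A separate research organisation handles study management and data capture, and its staff enter the data. Nothing says the sponsor sees outcomes while matching.

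What survives is the chart route. Section 7.1 collects existing record data without limiting it to baseline, a recurrence could already be recorded there, and no passage keeps that information from whoever chooses. It is also fair that a thin margin in events reflects rare recurrences and is not evidence of selection.

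**Conclusion.** The concern holds in a limited form. Control selection is described in two ways that the readable text does not reconcile. The inclusion decision rests with an interested party, and no order, lock date or blinding is stated. Outcome-aware selection is therefore not excluded; it is not shown to occur, and none is alleged. This is more than missing detail, because the stated procedure is itself discretionary and a less bias-prone one is cheap.

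The conclusion is sensitive to a few lesions: at the one-sided 0.05 that reproduces 293, the pass limit lies one (score) or two (Wald) events above a Mohs count of 4. A reversal by one or two lesions requires the result to sit close to that limit. The event counts treat the groups and lesions as independent, ignoring pairing and several lesions per patient. They also assume a confidence-bound or score test of the margin, since Section 12.2 names only Chi-square tests.

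**What to change.** Replace the two passages with one prespecified deterministic rule. One option:

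- Take eBx lesions in order of last treatment date, and match each to the eligible Mohs lesion, across all sites, that is nearest in treatment date. Break ties with a seeded random draw.
- Run the rule by program on a file holding only the matching variables, by someone without access to outcomes.
- Lock the resulting list, with ranked replacements for patients who decline or cannot be reached.
- Keep follow-up toxicities in the prospective data list only.

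Nearest date is one choice among several; what matters is that the rule leaves no discretion.

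Locking before any visit is probably no longer possible: Rev F is dated March 7, 2017 and first visits were planned from August 29, 2016. So apply the rule to pairs not yet matched, keep lesions already seen, and report a sensitivity analysis restricted to pairs matched under the locked rule.

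The cost is protocol wording and a short matching program. The downside is that the sensitivity analysis may rest on a smaller set of pairs.

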#### 8.3 Study Methodology Schema for Initial Follow-up Visits

Please see Figure 1 on page 14.

#### THIS SPACE INTENTIONALLY LEFT BLANK

#### 9 SITE REQUIRMENTS AND SELECTIONS

The sites will conduct the study following approval by an Institutional Review Board (IRB) and in accordance with 45 CFR 160 and 164 [Human Subjects Protection].

Sites selected have expressed an interest in the conduct of a controlled study to collect and report long-term outcomes and compare clinical outcomes of eBx versus Mohs surgery for the treatment of non-melanoma skin cancer.

Source worksheets will be used to collect data not found in the patients' records. The data from the source worksheets and the patient records will be entered into the EDC. ECR will have a unique user name and password, and the EDC system is 21 CFR 11 compliant.

#### 11 INVESTIGATOR RESPONSIBILITIES

The following responsibilities are required for investigators participating in this study:

- 1. Willingness to work with study project manager to facilitate study progress;
- 2. Adherence to applicable IRB requirements and willingness to comply with all applicable regulations and applicable good clinical practice guidelines;
- 3. Protocol compliance, including willingness to complete all relevant study documentation legibly;
- 4. Maintenance of confidentiality at all times;
- 5. Willingness to allow clinical monitors, at reasonable times agreed upon by the site and sponsor, to inspect all records pertaining to this trial; and
- 6. Willingness to agree to and sign the Investigator Agreement Page in this protocol indicating the protocol will be followed.

#### **12 STATISTICAL CONSIDERATIONS**

#### 12.1 Data Collection

Data will be collected at the study site on case report forms and will be entered into the online database by ECR personnel. The following data collection requirements are listed below:

Form # and Name	Retrospective Chart Review	Prospective Follow-up and Data Collection
Demographics and History	Х	
Eligibility	Х	
Treatment Planning and Treatment	Х	
Follow-up Including Cosmesis, Chronic Toxicities, Recurrence		Х
Patient Reported Outcomes (PRO) Survey		Х

#### Table 1. Case Report Forms

#### **12.2 Statistical Analyses**

This is a multi-center, retrospective-prospective study comparing non-melanoma skin cancer treatment (basal cell carcinoma and squamous cell carcinoma) using Xoft electronic brachytherapy (eBx) results compared to a Mohs micrographic surgery. The lesion data will be matched on 4 categories as outlined in Section 8 and the results will be compared between the two treatment groups.

A sample size calculation comparing treatment of NMSC with eBx to treatment with Mohs micrographic surgery was done using a 1.5% historical 3-year recurrence rate for NMSC treated with Mohs, and a 2.5% non-inferiority margin. A total of 293 lesions for each treatment group will provide 80% power with a 0.05 alpha level of significance. Data from up to three hundred-twenty (320) subjects with each type of treatment will be collected to ensure a sufficient number of lesions to adequately power the study. There may be more than one lesion per patient that is matched to another lesion in the other treatment group. The total lesions will be compared in this study and the lesion count determines the number of patients that are ultimately enrolled.

The primary endpoint of freedom from recurrence and the secondary endpoints will be summarized for each treatment group and Chi-square tests performed as applicable. All tests will be 2-sided, with significance level set at 0.05, and performed using SAS (version 9.4 SAS Institute, Inc., Cary, NC).

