#### 2 PROTOCOL SYNOPSIS

STUDY NAME	CTPR-0014 Rev F March 7, 2017: A Multi-Center Retrospective- prospective Matched Pairs Cohort Study to Assess Clinical Outcomes of Lesions Treated with eBx Compared to Lesions Treated with Mohs Surgery
CO-PRINCIPAL INVESTIGATORS	[name] and [name]
SITES	Up to 5 sites will participate
STUDY DESIGN	This is a retrospective-prospective study design. Patients who completed treatment approximately 3 years (range of 2-4 years) at time of initial IRB approval of this study will be identified and any existing data in the patient's record will be collected in addition to conducting office visits for long-term follow-up. The study will include 2 parts:
	1. Retrospective chart review: Collect data from patient records who completed treatment a minimum of 2 years prior to study onset and determine the feasibility of doing a matched pair cohort study comparison of eBx versus Mohs surgery. The history, demographic and treatment data will be retrospectively collected from up to 320 subjects previously treated with eBx for the treatment of NMSC and up to 320 subjects previously treated with Mohs surgery for the treatment of NMSC.
	2. Prospective Follow-up: Patients will return for long-term follow-up visits for the investigators to assess the lesion site, document absence of recurrence/ absence of recurrence, toxicities, and collect patient reported outcomes.
SAMPLE SIZE	Up to 640 patients who will return for follow-up approximately 2 to 5 years post treatment so that at least 586 lesions have long term follow-up data collected. Follow-up may range from approximately 2 to 5 years post treatment. Up to 2 visits may be completed by each subject, one in 2016, and one in 2017-2018.
STUDY OBJECTIVES	
 
To evaluate local recurrence of eBx and Mohs treated lesions.
 
To evaluate toxicities related to eBx and Mohs treatments.
 
To evaluate cosmetic outcomes for lesions treated with eBx and Mohs.
 
To assess the ability to deliver therapy with eBx and Mohs treatment modalities.
 

PRIMARY ENDPOINT	Absence of local recurrence at approximately 3 to 5 year follow-up (range is approximately two to five years) at treatment site(s).

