#### 7 STUDY DESIGN, ENROLLMENT, AND DURATION

#### 7.1 Study Design

This is a retrospective-prospective study design. Patients who completed treatment approximately 3 years (range of 2-4 years) at time of IRB approval of this study will be identified and any existing data in the patient's record will be collected in addition to conducting office visits for long-term follow-up.

The study will include:

Identifying patients, retrospectively, who completed treatment a minimum of 2 years prior to study onset. The history, demographic and treatment data will be collected from up to 320 subjects previously treated with eBx for the treatment of NMSC and up to 320 subjects previously treated with Mohs surgery for the treatment of NMSC. Data will be collected from enough patients to achieve the required sample size of 293 lesions in each treatment group. Patients will then return for long-term follow-up visit for the investigators to assess the lesion site, document absence of recurrence, chronic toxicities, and collect patient reported outcomes.

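### 293 lesions per group give 80% power only at one-sided 0.05; under the plan's two-sided 0.05 rule power is about 70%

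*Combined protocol and SAP*

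**What the plan says.** Section 12.2 (Statistical Analyses) sizes the study as a non-inferiority comparison of eBx with Mohs surgery, "using a 1.5% historical 3-year recurrence rate for NMSC treated with Mohs", "and a 2.5% non-inferiority margin". It concludes: "A total of 293 lesions for each treatment group will provide 80% power with a 0.05 alpha level of significance". That sentence does not say whether the alpha is one-sided or two-sided.

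The next paragraph turns to the analysis. The primary and secondary endpoints "will be summarized for each treatment group and Chi-square tests performed as applicable", and "All tests will be 2-sided, with significance level set at 0.05". It gives no separate rule for the primary comparison. The documents nowhere mention a one-sided test, a 90% interval or a non-inferiority bound.

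The target is repeated elsewhere. Section 7.1 collects data to "achieve the required sample size of 293 lesions in each treatment group", and the synopsis enrols patients "so that at least 586 lesions have long term follow-up data collected", which is 2 × 293.

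**The concern.** A sample size carries the stated power only for the test it was calculated for. A non-inferiority conclusion uses one side of the interval: the upper limit for the difference in recurrence (eBx minus Mohs) is compared with the margin. Under a two-sided 0.05 rule that is the upper limit of a 95% interval, with 0.025 in the tail. Under a one-sided 0.05 rule it is the upper limit of a 90% interval. The first is harder to meet and needs more lesions.

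If 293 came from the easier rule while the analysis follows the harder one, the 80% is overstated. If the easier rule is intended, the two-sided sentence is wrong for the primary endpoint. The plan as written supports either reading. If the choice is left until the data are known, the primary conclusion can depend on which reading is taken.

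**Working it through.** **Inputs**

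- Mohs recurrence p = 0.015 (Section 12.2).
- Margin d = 0.025 (Section 12.2). The scale is not stated; I read it as an absolute difference.
- Recurrence after eBx is not stated. I assume it equals the Mohs rate, 0.015.
- Equal groups of 293 lesions (Sections 7.1 and 12.2), treated as independent and unpaired.
- Power 80%, so z = 0.8416.

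**1. Reproduce the plan's figure**

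Lesions per group: n = (z_α + z_β)² × 2p(1 − p) / d².

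2 × 0.015 × 0.985 = 0.02955, and 0.02955 / 0.025² = 47.28.

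| Alpha in the non-inferiority direction | z_α | (z_α + z_β)² | n | Rounded up |
|---|---|---|---|---|
| 0.05 (one-sided 0.05) | 1.6449 | 6.183 | 292.3 | **293** |
| 0.025 (two-sided 0.05) | 1.9600 | 7.849 | 371.1 | **372** |

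One-sided 0.05 matches the plan exactly. None of the other constructions tried gives 293:

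| Construction | n per group |
|---|---|
| Continuity-corrected non-inferiority, one-sided 0.05 / 0.025 | 368 / 448 |
| Farrington-Manning variance, one-sided 0.05 / 0.025 | 376 / 484 |
| Two one-sided tests for equivalence, 0.05 each side | 405 |
| Superiority, 1.5% against 4.0%, one-sided / two-sided | 529 / 671 |
| The same with continuity correction | 606 / 749 |

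**2. Power with 293 lesions under each rule**

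Power = Φ(d/SE − z_α), with SE = √(0.02955/n).

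At n = 293, SE = 0.010043 and d/SE = 2.489.

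- One-sided 0.05: Φ(2.489 − 1.645) = Φ(0.844) = 80.1%.
- Two-sided 0.05: Φ(2.489 − 1.960) = Φ(0.529) = 70.2%.

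At n = 320 lesions, d/SE = 2.602 and the two figures are 83.1% and 73.9%.

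**3. Check on the approximation**

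Only 293 × 0.015 = 4.4 recurrences are expected per group, so I also enumerated the binomial outcomes exactly at n = 293:

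| Test | One-sided 0.05 | One-sided 0.025 |
|---|---|---|
| Normal approximation | 80.1% | 70.2% |
| Wald test, exact | 81.9% | 69.6% |
| Farrington-Manning score test, exact | 71.8% | 57.3% |

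Changing the alpha costs 10 percentage points or more with every method.

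**4. Can the choice change the conclusion?**

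Take 6 recurrences after eBx and 4 after Mohs, with 293 lesions each. This is an illustration, not trial data.

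- Difference: 2/293 = 0.683%.
- Wald standard error: √[(0.02048 × 0.97952 + 0.01365 × 0.98635)/293] = 1.070%.
- Upper limit, 90% interval: 0.683 + 1.645 × 1.070 = 2.44%, below 2.5%, so non-inferior.
- Upper limit, 95% interval: 0.683 + 1.960 × 1.070 = 2.78%, above 2.5%, so not shown.

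**The case against.** The arithmetic is not in dispute. The best case on the other side concerns what it is applied to.

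- **The plan names no non-inferiority test.** An ordinary two-sided chi-square test addresses equality, not a margin, so the 70% belongs to an interval that I have supplied. The two-sided sentence might also have been meant only for the chi-square comparisons just before it. The first point stands: the test has to be named. The second is weak, because the sentence covers every test and directly follows one that names the primary endpoint. If non-inferiority was meant to be exempt, the plan must say so.
- **Both power figures depend on the method.** This stands. With a score test, 293 lesions give 71.8% at one-sided 0.05 and 57.3% at 0.025. With true rates of 4.0% (eBx) and 1.5% (Mohs), the exact false-positive rate of the Wald test is about 6.9% at nominal 5% and 3.5% at nominal 2.5%; the score test gives 4.6% and 2.2%. A corrected power figure therefore needs its method beside it.
- **Equal recurrence is an assumption.** Power is sensitive to it. At two-sided 0.05 with 293 lesions, a true eBx rate of 1.25% gives 81.6% and 1.75% gives 57.7%. But the equal-rate assumption reproduces 293 exactly, so it is very probably the sponsor's own.
- **The limit of 320 is on subjects, not lesions.** This is correct, and 293 is a minimum. At 372/320 = 1.16 matched lesions per subject, the cap could supply 372 lesions. The documents give no such ratio, and the stated target remains 293.
- **Power does not affect validity.** True, but the unresolved choice between a 90% and a 95% interval does affect the decision.

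**Conclusion.** The concern holds. The 80% belongs to a one-sided 0.05 non-inferiority test, while the plan states a two-sided 0.05 rule for all tests. Under that rule 293 lesions per group give 70.2% power, and 80% would need 372 per group (744 in total). The false-negative risk is about 30% instead of 20%.

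These figures assume true recurrence of 1.5% in both groups, a margin on the absolute scale, a Wald-type bound, and independent, unpaired lesions. The documents give no within-patient correlation and no discordance between matched pairs, so the effect of matching and of several lesions per patient cannot be computed. The conflict between the two sentences does not depend on those quantities.

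It must be settled before analysis because it concerns the success rule for the primary endpoint.

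**What to change.** Keep 293 lesions per group and make the two statements in Section 12.2 agree in one of two ways.

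1. **Preferred.** Keep two-sided 0.05. State that non-inferiority is concluded if the upper limit of the 95% interval for the difference in recurrence is below 2.5 percentage points. Restate power at 293 per group as about 70% under the sponsor's formula.
2. **Alternative.** Exempt the primary comparison from the two-sided sentence. State that it is tested one-sided at 0.05 with a two-sided 90% interval, for which 80% is correct under the sponsor's formula.

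Under either option, name the interval or test method, and state the assumed eBx rate and the scale of the margin, so that the power figure can be reproduced. If a score method is chosen, quote its own power: about 57% under option 1 or 72% under option 2.

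The cost is a corrected sentence plus those details. No extra patients are needed, and the figures of 293 and 586 elsewhere stay as they are. The price is a less favourable stated power under option 1, or an openly one-sided alpha of 0.05 under option 2.

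### At 293 lesions per group, no unmatched test examined gives both the stated 80% power and the stated 0.05 error rate; a score test has about 72% power at one-sided 0.05

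*Combined protocol and SAP*

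**What the plan says.** Section 12.2 bases the sample size on a "1.5% historical 3-year recurrence rate for NMSC treated with Mohs, and a 2.5% non-inferiority margin". It then concludes: "A total of 293 lesions for each treatment group will provide 80% power with a 0.05 alpha level of significance". Section 7.1 repeats the number as a requirement ("to achieve the required sample size of 293 lesions in each treatment group").

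The section does not give the formula, the assumed eBx rate, the scale of the margin, or whether the alpha used for sizing is one- or two-sided. It names no non-inferiority test and no confidence interval. On analysis it says only that the endpoints "will be summarized for each treatment group and Chi-square tests performed as applicable", and then: "All tests will be 2-sided, with significance level set at 0.05".

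On structure, Section 8.2 says: "Each lesion from the eBx treatment group will be matched to a lesion treated with Mohs surgery". Section 12.2 makes the lesion the unit of comparison and allows a patient to contribute more than one.

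**The concern.** The plan attaches two properties to 293 lesions per group: 80% power and an error rate of 0.05. The number appears to come from a large-sample formula, yet the design expects only 293 × 0.015 = 4.4 recurrences per group. With so few events, a Wald test can reject too often at the margin and so look more powerful than a test that holds its level.

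If that happens here, one of the two properties is missing. Either the chance of showing non-inferiority is overstated, or the chance of wrongly declaring it is understated. Because no test is named, the plan does not show which. Nor does it prevent the method from being settled after the counts are known.

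**Working it through.** **Inputs.** From Section 12.2: Mohs rate 1.5%, margin 2.5%, 293 per group, power 80%, alpha 0.05. From Section 8.2: 1:1 allocation. Assumed, because the documents are silent: the margin is in absolute percentage points, the true eBx rate equals the Mohs rate, and lesions are independent and unmatched.

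**Step 1: reproduce 293.** The unpooled Wald formula with equal true rates is n = (z₁₋α + z₁₋β)² × 2p(1−p) / margin².

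- One-sided 0.05: (1.645 + 0.842)² × 2 × 0.015 × 0.985 / 0.025² = 292.3, so 293.
- One-sided 0.025: 371.1, so 372.
- Farrington-Manning score formula: 376 at one-sided 0.05 and 484 at one-sided 0.025.
- Superiority of 1.5% against 4.0%: 529 one-sided, 671 two-sided.

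Of these, only the first gives 293.

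**Step 2: exact operating characteristics at 293 per group.** For each test, list every pair of counts (eBx, Mohs) that would declare non-inferiority. Then sum the product of the two binomial probabilities over those pairs. Power is taken at 1.5% in both groups. Type I error is taken at the margin, with Mohs 1.5% and eBx 4.0%.

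- Wald declares non-inferiority when (0.025 − d)/SE reaches the critical value, where d is the observed eBx minus Mohs difference and SE uses the observed proportions.
- Farrington-Manning uses the same numerator, but its SE comes from proportions estimated under the constraint that eBx exceeds Mohs by exactly 0.025.

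| Test | One-sided alpha | Power | Type I error |
|---|---|---|---|
| Wald | 0.05 | 81.9% | 6.85% |
| Agresti-Caffo | 0.05 | 76.9% | 5.5% |
| Farrington-Manning | 0.05 | 71.8% | 4.6% |
| Newcombe interval | 0.05 | 71.8% | 4.6% |
| Wald | 0.025 | 69.6% | 3.5% |
| Farrington-Manning | 0.025 | 57.3% | 2.2% |

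The exact unconditional test at one-sided 0.05 has 71.7% power. No row combines 80% power with an error rate at or below its nominal level.

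**Step 3: does the choice of test matter for plausible data?** Take 6 eBx and 4 Mohs recurrences out of 293 each, so d = 2/293 = 0.0068.

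- Wald: SE = 0.0107 and z = (0.025 − 0.0068)/0.0107 = 1.70. This exceeds 1.645, so non-inferiority is declared.
- Farrington-Manning: constrained rates 3.46% and 0.96%, SE = 0.0121, z = 1.50. Non-inferiority is not declared.

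Counts of 5 and 3 also split (z = 1.90 and 1.60). These counts lie close to the 4.4 per group that the plan expects.

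**Step 4: is this peculiar to 293 or to 1.5%?** For n from 281 to 305, score-test power runs from 68% to 75% and Wald error from 5.9% to 6.9%. At n = 293 with equal true rates of 0.5% to 2.5%, Wald error runs from 9.5% down to 6.0%, while Farrington-Manning stays between 4.1% and 4.9%. Score-test power depends on the rate: 82% at 1.0%, 72% at 1.5%, 63% at 2.0%. Exact score-test power reaches 80% from about 354 lesions per group and stays there up to 419, the largest n checked.

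**The case against.** **The arithmetic of 293 is sound.** This stands. The number is exact under a standard formula, and sizing by a normal approximation is common. A reader might infer a computing mistake; the documents do not support that. The problem is the power and error rate attached to the number.

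**A 7% error rate describes a test that the plan never names.** This also stands. A reader might infer that the trial will run at about 7%. The Wald origin is inferred from a numerical match, and Section 12.2 names only chi-square tests. The 6.9% applies if a Wald non-inferiority test is used.

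**The design is matched, so unmatched figures may mislead.** This stands in part. A reader might infer that no test whatever could deliver both figures; that is not shown. A simulated matched-pair score test (Tango) at 293 pairs and one-sided 0.05 has power of about 72%, 75%, 78% and 81% at within-pair correlations of 0, 0.1, 0.2 and 0.3, with error below 5% throughout. Those correlations are assumptions, and 0.3 is high for rare recurrences in different patients. Several lesions per patient would usually push power the other way.

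**293 is a minimum, and up to 320 subjects per group may be enrolled.** The 320 is a ceiling on subjects, not a target for lesions. At 320 independent lesions per group, score-test power at one-sided 0.05 is 77.2%. The gap narrows but does not close, and Section 12.2 claims 80% at 293.

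**The sidedness conflict is the larger problem.** It is a separate one. A reader might charge the whole fall to 57% to the approximation. In fact the move to one-sided 0.025 alone takes Wald power from 81.9% to 69.6%, and the change of test accounts for the rest. Resolving sidedness leaves Wald error above nominal at either level (6.85% against 5%; 3.5% against 2.5%).

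**Conclusion.** The statement in Section 12.2 does not hold as written for any unmatched test examined. At 293 per group and one-sided 0.05, about 80% power comes with about 6.9% type I error, while a score test that holds its level has about 72% power. The miscalibration is moderate, but it bears on the primary comparison.

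The result rests on a 2.5-point absolute margin, true rates of 1.5% in both groups, and independent, unmatched lesions. Matching and clustering could move the power in opposite directions, and the documents give no figure for either.

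**What to change.** In Section 12.2:

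- Name a score-based non-inferiority test and confidence interval for the difference in recurrence: Farrington-Manning or Miettinen-Nurminen, or a matched-pair score version.
- State its one-sided alpha, reconciled with the two-sided 0.05 in the same section.
- Replace 80% with the power of the named test at 293 per group: about 72% at one-sided 0.05, or about 57% if two-sided 0.05 is kept. State beside it that lesions are taken as independent and unmatched. If a matched-pair test is chosen, state the within-pair correlation assumed.

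The cost is a change of wording and a less favourable stated power. No added patients are needed. Only if the sponsor wishes to keep 80% with an unmatched score test at one-sided 0.05 would the number rise, to about 354 lesions per group.
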